6.1.3. Per-Protocol Set for analysis of efficacy (PPS for efficacy)

For the primary analysis up to month 14, the PPS for efficacy will include all subjects from the ES who fulfilled eligibility criteria and who received all vaccinations according to protocol procedures within the protocol specified intervals that contribute to the time at risk in the follow-up period starting 14 days post-Dose 3.

For the final analysis up to month 50, all subjects who have not received Dose 4 of study vaccine or subsequent yearly doses (Dose 5 and Dose 6) according to protocol will be censored at the last contact date prior to the first missed dose recorded and will contribute to the PPS analysis up to censoring.

6.1.4. Per-Protocol Set for analysis of immunogenicity (PPS for immunogenicity)

The PPS for immunogenicity will include all subjects included in the ES who received all vaccinations according to protocol procedures within the protocol specified intervals, performed blood samplings for immunogenicity according to protocol intervals, met all eligibility criteria, did not use any medication or blood products forbidden by the protocol and did not have any reported underlying medical condition influencing immune responses.

6.1.5. Solicited Safety Set

The solicited safety set- including the solicited safety set within the reactogenicity sub cohort- will include all subjects who received at least one dose of study vaccine and had solicited safety data.

6.2. Criteria for eliminating data from Analysis Sets

Elimination codes are used to identify subjects to be eliminated from analysis. Detail is provided below for each set.

6.2.1. Elimination from Exposed Set (ES)

Code 1030 (study vaccine not administered at all), code 800 (fraudulent data) and code 900 (invalid informed consent) will be used for identifying subjects eliminated from the ES and the reactogenicity sub-cohort.

6.2.2. Elimination from the PPS for analysis of efficacy and immunogenicity

A subject will be excluded from the PPS under the following conditions:

Code	Condition under which the code is used	Visit (timepoints) where the code is applicable	Applicable analysis set
800	Fraudulent data	All visits	immunology, efficacy
900	Invalid informed consent	All visits	immunology, efficacy
1030	Study vaccine not administered at all but subject number allocated Subject randomized but not vaccinated.	Visit 2, and onwards	immunology, efficacy
1040*	Administration of concomitant vaccine(s) forbidden in the protocol to be determined by CRDL from review of individual data listings	For efficacy set (3035 elimination code): a vaccine not foreseen by the study protocol administered during the period starting seven days before each dose and ending seven days after each dose of vaccine. It applies only for the three first doses.	immunology, efficacy
1050	Randomisation failure First vaccination not equal to the group the subject was randomized to. To be attributed by Statistician and CDR: check SBIR, replacement, vaccine administration	Time of randomization, and onwards	immunology, efficacy

C :	Statistical Analysis Pla		
Code	Condition under which the code is used	Visit (timepoints) where the code is applicable	Applicable analysis set
1070*	Vaccination not according to protocol: Incomplete vaccination course before treatment withdrawal Wrong replacement or study vaccine administered (not compatible with the vaccine regimen associated to the treatment number).	All visits were vaccinations are planned: • Control → Visit 2, 3 and 4 • R012-20 → Visit 2, 3, 4 and 24 • R012-14 → Visit 2, 3, 4, 18, 27 and 33 • Fx012-14 → Visit 2, 3, 4, 18, 27, and 33 • Fx017-20 → Visit 2, 3, 10, 24 and 30	immunology
1080*	Vaccine temperature deviation vaccine administered despite a Good Manufacturing Practices (GMP) no-go temperature deviation	For efficacy set (3075 elimination code): applies at the time of the first 3 doses. For control, R012-20, R012-14 and Fx012-14 at visit 2,3 and 4. For Fx017-20 at visit 2,3 and 7.	Immunology, efficacy
1090*	Expired vaccine administered	For efficacy set (3090 elimination code): applies at the time of the first 3 doses. For control, R012-20, R012-14 and Fx012-14 at visit 2,3 and 4. For Fx017-20 at visit 2,3 and 7.	Immunology, efficacy
2010	Protocol violation (inclusion/exclusion criteria) including age Subject's age should be 5- 17 months at first study visit.	Visit 2 • Subjects for whom date of birth → Visit 2 is outside [5-17 months] • All other criteria that are not met	Immunology, efficacy
2040*	Administration of any medication forbidden by the protocol To be determined by CRDL from review of individual data listings	For the efficacy set (3040 elimination code): A vaccine not foreseen by the study protocol administered during the period starting seven days before each dose and ending seven days after each dose of vaccine. It applies only for the three first doses	Immunology, efficacy

			cal Analysis Plan
Code	Condition under which the code is used	Visit (timepoints) where the code is applicable	Applicable analysis set
2080*	Subjects did not comply with vaccination schedule vac1=first vaccination, vac2 = second vaccination etc.	For the immuno set it applies under following conditions: • All groups: vac1→vac2 is outside [21-35 days] • Control, R012-20, R012-14, Fx012-14: vac2→vac3 is outside [21-35 days] • R012-20: vac3→vac4 is outside [518-574 days] • R012-14, Fx012-14: vac3→vac4 is outside [336-392 days] vac4→vac5 is outside [336-392 days] vac5→vac6 is outside [336-392 days] • Fx017: vac2→vac3 is outside [161-203 days] vac3→vac4 is outside [364-420 days] vac4→vac5 is outside [336-392 days] For efficacy set (3080 elimination code) it applies to the time of the first 3 doses. For control, R012-20, R012-14 and Fx012-14 at visit 2,3 and 4. For Fx017-20 at visit 2,3 and 7.	Immunology, efficacy
2090*	Subjects did not comply with blood sample schedule Ser1=first serum collection, ser2 = second serum collection etc. +For these intervals, calculations were done by adding up both minimum and maximum days of the	 Applies under following conditions: Control, R012-20, R012-14, Fx012-14: vac3→ser3 (M3) is outside [21-35 days] Control: 	Immunology

Codo	Statistical Analy		
Code	Condition under which the code is used	Visit (timepoints) where the code is applicable	Applicable analysis set
	visit intervals specified in table 14 of the protocol	vac3→ser4(M20) is outside [518- 574 days]	
		vac3→ser5 (M50) is outside [+1316-1596 days]	
		• R012-20:	
		vac4→ser5 (M21) is outside [21-35 days]	
		vac4→ser6 (M50) is outside [+812-1008 days]	
		• R012-14, Fx012-14:	
		vac4→ser5 (M15) is outside [21- 35 days]	
		vac5→ser7 (M27) is outside [21- 35 days]	
		vac6→ser9 (M34) is outside [21- 35 days]	
		vac6→ser10 (m50) is outside [+308-420 days]	
		• Fx017- 20:	
		vac2→ser2(M2) is outside [21-35 days]	
		vac3→ser4 (M8) is outside [21-35 days]	
		vac4→ser6 (M21) is outside [21- 35 days]	
		vac5→ser7 (M33) is outside [21- 35 days]	
		vac5→ser9 (M50) is outside [+476-616 days]	
2100	Serological results	All visits where serum samples are	Immunology
	not available post-	planned (see Table 1– time points for	
	vaccination if ALL are missing and subject in Immunogenicity	immunogenicity)	
2120	Subset	All vigits where some someles are	Immunalagy
2120	Incomplete assessment and mislabelling (sample	All visits where serum samples are planned (see Table 1– time points for immunog enicity)	Immunology
	tested/not tested) of		

Code	Condition under which the code is used	Visit (timepoints) where the code is applicable	Applicable analysis set
	blood sample, for specific assays		

Code	Condition under which the code is used	Visit (timepoints) where the code is applicable	Applicable analysis set
3100	Subjects without follow up data starting 14 days post dose 3 Note that subjects not receiving dose 4, 5 and 6 will be censored at the last contact prior to whichever first missed dose recorded	 Applies under following conditions: First 3 vaccinations are administered No data available 14 days after visit 4 for Control, R012-20, R012-14, Fx012-14 No data available 14 days after visit 10 for Fx017-20 	Efficacy
3200	Subjects not receiving first 3 doses	 Applies under following conditions For control, R012-20, R012-14, Fx012-14 → no vaccination administered at visit 2,3 and 4. For Fx017-20 → no vaccination administered at visit 2,3 and 10 	Efficacy

^{*}a Dynamic elimination approach will be used for the definition of the immunogenicity PPS (Analysis M21 E1_02, Analysis M33 E1_03, Final analysis). This means that for codes 1040, 1070, 1080,1090, 2080, only the data relevant/posterior to the deviation will be eliminated. For codes 2040, 2090, 2120, the data elimination will be visit specific. For the efficacy PPS subjects will be fully excluded based on the elimination codes. However, subjects included in the efficacy analysis could be censored at last contact date.

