11.5.2. ATP cohort for efficacy

The ATP cohort for efficacy will include all subjects included in the TVC who fulfilled eligibility criteria and who received all vaccinations according to protocol procedures within the protocol specified intervals that contribute to the time at risk in the follow-up period starting 14 days post-Dose 3. Subjects who have not received Dose 4 of study vaccine or subsequent yearly doses (Dose 5 and Dose 6) according to protocol will be censored at the last contact date recorded and will contribute to the ATP analysis up to censoring.

Of note, subjects with a prevalent *P. falciparum* infection at the beginning of the follow-up period will not be included in the ATP analysis of vaccine efficacy against first or only incident *P. falciparum* infection. Sensitivity analyses by left censoring (i.e. start of follow up defined as first negative ADI visit for all children) will be performed.

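### SAP 6.2.2: no efficacy elimination code covers a wrong study vaccine or volume at dose 2 or 3, and three codes list Visit 7 for Fx017-20, where no vaccine is given

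*SAP*

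**What the plan says.** **Definition.** SAP 6.1.3 admits to the efficacy PPS children "who received all vaccinations according to protocol procedures within the protocol specified intervals". Protocol 11.5.2 has the same rule for its ATP cohort for efficacy: children "who fulfilled eligibility criteria and who received all vaccinations according to protocol procedures".

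**Implementation.** SAP 6.2 states: "Elimination codes are used to identify subjects to be eliminated from analysis". The footnote to the table in SAP 6.2.2 adds: "For the efficacy PPS subjects will be fully excluded based on the elimination codes".

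**Wrong study vaccine.** Code 1070 covers an incomplete course and, in its second half, "Wrong replacement or study vaccine administered (not compatible with the vaccine regimen associated to the treatment number". Its applicable set is immunology only.

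**Nearest efficacy codes.**
- Code 1050 applies under the condition "First vaccination not equal to the group the subject was randomized to". Its row adds an instruction: "To be attributed by Statistician and CDR: check SBIR, replacement, vaccine administration".
- Code 3035 covers "a vaccine not foreseen by the study protocol administered during the period starting seven days before each dose" (and the week after).
- Code 3200 covers scheduled doses that were not given.

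**Visit lists.** Codes 3075 (temperature deviation), 3090 (expired vaccine) and 3080 (vaccination interval) each say that they cover the first three doses. Each then lists Visits 2, 3 and 7 for Fx017-20. Codes 1070, 3100 and 3200 use Visit 10 for that group's third dose.

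**Grouping.** SAP 6.1.2 says that the Exposed Set (ES) is analysed by treatment actually administered. SAP 6.1.3 does not say how the PPS is grouped.

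**The concern.** The primary analysis compares Fx012-14 with the two pooled R012 groups in the efficacy PPS over Months 2.5 to 14. Protocol Table 23 shows that, up to Month 14, these groups differ by plan only in the volume of the third dose (0.1 ml or 0.5 ml). Protocol 7.3.1 has both volumes drawn from the same vial presentation. The efficacy codes check temperature, expiry and timing of the third dose, but not the exposure under test.

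If misdosed children stay in the set under their randomised arm, the contrast is diluted. If the sponsor relies on the wording of 6.1.3 without a code, exclusions would have to be decided case by case in an open-label trial.

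The Visit 7 entry has a different reach. Programmed literally, it would leave third-dose temperature, expiry and interval deviations unchecked in Fx017-20 while they are checked in every other arm. It does not touch the primary comparison. It does touch Fx017-20 versus three full doses over 12 months post-dose 3, the one secondary comparison that SAP section 8 places under hierarchical alpha control.

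**Working it through.** **1. Do the codes cover a wrong vaccine or volume?** SAP 6.2.2 has 16 code rows, of which 12 apply to efficacy.

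| Efficacy code | What it tests | Wrong study vaccine at dose 2 or 3? |
|---|---|---|
| 800, 900, 1030 | Fraud, consent, never vaccinated | No |
| 1050 | First vaccination against randomised group | No, dose 1 only |
| 2010 | Eligibility | No |
| 1040/3035, 2040/3040 | Unforeseen vaccine, forbidden medication | No |
| 1080/3075, 1090/3090 | Temperature, expiry | No |
| 2080/3080 | Interval between doses | No |
| 3100 | No follow-up from 14 days after dose 3 | No |
| 3200 | Dose not given | No |

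Code 1050 cannot separate the RTS,S arms, because the first vaccination is the same full dose in all four (protocol Table 23). Its instruction to check vaccine administration sits under that first-vaccination condition.

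The SAP's document history explains that the second version created separate efficacy codes so that only the first three doses count. Codes 1040, 1080, 1090, 2040 and 2080 received counterparts. Code 1070 did not. Code 3200 picks up only its missed-dose half.

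**2. Which visit is the third dose in Fx017-20?** Protocol Table 15 has Visit 7 at Month 4, with a parasitemia sample and nothing else. Protocol Table 23 has the third dose at Visit 10, Month 7. The cells for 3075, 3080 and 3090 therefore contradict their own first-three-doses rule. A slip for Month 7 is the likely explanation.

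**3. Size of the dilution.** The inputs from protocol 11.4 are R = 0.29 and F = 0.16 episodes per person-year, with a stated incremental efficacy of 50%. The two rates give 1 − 0.16/0.29 = 1 − 0.552 = 44.8%, not 50%, so both values are carried. To obtain 50% with R = 0.29, F = 0.145.

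The assumption is that a share q of children receives the other arm's third dose and is analysed in the randomised arm. The documents give no rate, so q = 2% and 5% are illustrations.

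- Errors in Fx012-14 only: F′ = F(1 − q) + Rq, and efficacy = 1 − F′/R.
- Errors in both directions: also R′ = R(1 − q) + Fq, and efficacy = 1 − F′/R′.

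| Starting efficacy | q | Fx012-14 only | Both directions |
|---|---|---|---|
| 44.8% | 2% | 1 − 0.1626/0.29 = 43.9% | 1 − 0.1626/0.2874 = 43.4% |
| 44.8% | 5% | 1 − 0.1665/0.29 = 42.6% | 1 − 0.1665/0.2835 = 41.3% |
| 50.0% | 2% | 1 − 0.1479/0.29 = 49.0% | 1 − 0.1479/0.2871 = 48.5% |
| 50.0% | 5% | 1 − 0.15225/0.29 = 47.5% | 1 − 0.15225/0.28275 = 46.2% |

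The loss runs from 44.8 − 43.9 = 0.9 to 50.0 − 46.2 = 3.8 percentage points. If children are grouped by vaccine received, it is zero.

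**4. Why no power claim.** Take 500 versus 250 children, 11.5 months of follow-up, and rates of 0.29 and 0.16 with no dosing errors. Expected first events are 500(1 − exp(−0.29 × 11.5/12)) = 121.3 and 250(1 − exp(−0.16 × 11.5/12)) = 35.5. Two-sided 5% power is 94.0% by the Schoenfeld formula, or 87.7% with the Wald variance 1/121.3 + 1/35.5. The choice of formula moves power by more than most of the error scenarios do (Schoenfeld: 92.8% and 90.8% for errors in Fx012-14 only, 91.9% and 87.9% for errors in both directions).

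**The case against.** The strongest reply is that the rule already exists. SAP 6.1.3 excludes such children whatever the table says. The footnote on full exclusion is there to contrast the efficacy set with the dynamic, partial elimination used for immunogenicity, and it does not declare the table exhaustive. That is a fair reading of the footnote's purpose. But the table and SAP 6.2 are the only stated means of identifying excluded children, and the definition and its implementation still disagree.

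Second, code 1070 speaks of study vaccine, not volume. The point is literally correct. However, the full dose and the 1/5th dose are separate named treatments in the protocol, and 1070's general heading is vaccination not according to protocol, so including volume is a reasonable reading.

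Third, the Protocol Deviation Management Plan may classify dosing errors. It was not available here. SAP 6.3 cites it only for deviations that do not lead to elimination.

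Fourth, the same contrast is also run on the ES from Day 0 to Month 14, by treatment actually administered (SAP 7.3.1.6 and 6.1.2). This is a useful cross-check, but it is a secondary analysis with a different set and start date, and it does not settle who belongs in the primary set.

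Fifth, the effect is small. The 3.8-point figure needs 5% errors in both directions, randomised-arm grouping and the stated 50%. At 2% and the protocol's own rates the loss is 0.9 to 1.4 points (44.8 − 43.4 = 1.4). Protocol 6.2.2.2.2 also has the randomization system issue a group-consistent treatment number at each dose. All of this stands, and it limits the size. The system does not, however, verify the volume drawn.

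On Visit 7, a literal lookup would find no vaccination and so might expose the slip. That is plausible, but the cells should not depend on it.

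**Conclusion.** Both parts hold. By the codes as written, a child given the wrong study vaccine or volume at dose 2 or 3 remains in the efficacy PPS, contrary to SAP 6.1.3 and protocol 11.5.2. Three efficacy codes name a visit at which Fx017-20 receives no vaccine.

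The numerical effect of the first part is unknown and probably small: 0.9 to 3.8 percentage points of incremental efficacy under assumed error rates of 2% to 5% with randomised-arm grouping, and none if grouped by vaccine received. Dilution acts toward no difference, so it cannot create a false superiority claim. No deviation rate is given for the second part, so no size can be stated. It bears on the Fx017-20 analyses only.

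The case for correcting the plan rests on the contradiction in how the primary set is built, more than on the likely size of the bias.

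**What to change.** 1. Add to SAP 6.2.2 an efficacy counterpart of the wrong-vaccine half of code 1070, naming both vaccine and volume and limited to the first three doses.
2. State in one sentence whether the efficacy PPS is grouped by randomised arm or by vaccine received.
3. Reconcile the Fx017-20 visit lists in codes 3075, 3080 and 3090 with Visit 10 as used in codes 1070, 3100 and 3200 and in protocol Table 23.
4. If the Protocol Deviation Management Plan already classifies dosing errors, refer to it in the table.

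The cost is a table edit, one sentence, minor elimination-code programming, and possibly a few fewer children in the PPS. No trial procedure changes.

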6.2.3. Elimination from solicited safety set

Code 1030 (study vaccine not administered at all), code 800 (fraudulent data) and code 900 (invalid informed consent) and code 1160 (no post-vaccination solicited safety data) will be used for identifying subjects eliminated from the solicited safety set and subjects of the solicited safety set who are part of the reactogenicity sub-cohort.

6.3. Protocol deviation not leading to elimination from perprotocol analysis set

Protocol deviations not leading to elimination from PPS analyses are defined in the MALARIA-094 Protocol Deviation Management Plan.

https://biodocumentum.bio.corpnet1.com/webtoppr/drl/objectId/090f45f6898bbf02 (MALARIA-094 (204889) Protocol Deviation Management Plan V3 corrected on 22 Aug 2019 (09-Jul-2019))

7. STATISTICAL ANALYSES

Note that standard data derivation rules and stat methods are described in the annex and will not be repeated below. The study specific data derivation rules and stat methods will be described in section 11.1.

7.1. Demography

7.1.1. Analysis of demographics/baseline characteristics planned in the protocol

A study flow diagram (consort) will be generated to present the number of subjects screened, randomized, receiving doses and included in the PPS analyses.

Demographic characteristics (age and gender) and the baseline hemoglobin level will be tabulated per study group overall, and by site, for each cohort (ES, PPS cohort for efficacy and PPS cohort for immunogenicity).

The mean age at first vaccination (in months) (plus range and standard deviation [SD]) of the vaccinated subjects as a whole, and per group, will be calculated.

7.1.2. Additional considerations

Demographic characteristics, cohort description, withdrawal status will be summarized by group using descriptive statistics:

- Frequency tables will be generated for categorical variables such as gender.
- Mean, median, SD, minimum and maximum will be provided for continuous data such as age.
- The withdrawal status will be summarized by group using descriptive statistics.
- The number of subjects enrolled into the study as well as the number of subjects excluded from PPS analyses will be tabulated.
- The numbers of withdrawn subjects will be tabulated according to the reason for withdrawal.

7.2. Exposure

The number and percentage of subjects who received study vaccine doses will be tabulated overall for each study group separately (ES).

7.3. Efficacy/Effectiveness

7.3.1. Analysis of efficacy planned in the protocol

The primary analysis of efficacy will be based on the PPS for efficacy. The effect of the vaccine will be characterized using different complementary standard methodologies.

7.3.1.1. Strategy of analysis and rationale

The strategy of analysis for the present study has been developed considering the following points:

- Prevalent infections are only captured by ADI during the cross-sectional surveys performed at pre-defined timepoints throughout the study. Incident infections are captured via both ADI at cross-sectional surveys and via passive detection upon spontaneous presentation at health centers (see Section 4.2 of the protocol for case definitions of *P. falciparum* infections). Episodes of clinical malaria will be treated when diagnosed. Samples collected at cross-sectional visits in asymptomatic children will not be processed in real time and will not lead to systematic treatment.
- Vaccine efficacy against prevalent *P. falciparum* infections at the successive cross-sectional surveys is an important measure as it is not influenced by care seeking behavior and possibly less influenced by blood-stage immunity. Reducing the prevalence of blood-stage infections at successive timepoints will be a good indicator of the potential to reduce transmission as it is directly associated with the potential to infect mosquitoes.
- Vaccine efficacy against first or only episode of incident *P. falciparum* infection or against first or only episode of clinical malaria minimizes the bias related to differential acquisition of blood-stage immunity in the vaccine and Control groups, and is assumed to be the best way to assess the biological effect of the third dose fractioning and spacing.
- Vaccine efficacy against all episodes of clinical malaria is more relevant to public health but over longer time periods. There is a possibility of bias related to the fact that it will compare a Control group with frequent exposure and an intervention group with reduced exposure and a different build-up of blood-stage immunity over time, possibly influencing health seeking behaviors (hence the importance of also evaluating vaccine efficacy against prevalent infection and first or only episode).
- Considering the measures of incidence:
 - For group comparisons with identical calendar time follow-up periods, the incidence rates will be directly compared. The incremental vaccine efficacy estimate is defined as 1-Incidence Rate Ratio in each group.
 - When different calendar time follow up periods are compared, as is done for comparison Fx017 versus both Fx012 and R012 during the period 7 and 12 months post dose 3, the following analysis will be performed:
- 1. An analysis comparing the treatment schedules Fx017-20 versus Fx012-14 and R012-14 with respect to clinical malaria and incident infection taking into account potential confounders. The following covariates are considered to be prognostic for clinical malaria: monthly prevalence of parasitemia for control group and study site. An example will be described for comparison Fx017-20 versus both Fx012-14 7 months post dose 3. For the analysis with outcome first or only episode of clinical malaria, a cox regression with outcome time to clinical malaria will be modeled, with treatment as exposure (comparing schedule Fx012-14 from month 2-9 versus Fx017-

20 from month 7-14), monthly prevalence of parasitemia for control group as covariate (continuous) and study site (Ghana versus Kenya). For the analysis with all episodes of clinical malaria, a negative binomial regression (method described in section 7.3.1.2) will be performed. The same exposures and covariates as used for the cox regression will be entered in this model. The adjusted incremental efficacy will be defined as 1 minus the hazard ratio/incidence ratio, during the corresponding time frame for first or only episode/all episodes.

 The estimation of the number of cases of clinical malaria averted will inform on how the vaccine efficacy translates into impact, in a way that is dependent on exposure and hence transmission intensity.

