5.2. Inclusion criteria for enrolment

Deviations from inclusion criteria are not allowed because they can potentially jeopardize the scientific integrity of the study, regulatory acceptability or subject safety. Therefore, adherence to the criteria as specified in the protocol is essential.

All subjects must satisfy ALL the following criteria at study entry:

- Subjects' parent(s)/LAR(s) who, in the opinion of the investigator, can and will comply with the requirements of the protocol (e.g. return for follow-up visits).
- Signed or thumb-printed and witnessed informed consent obtained from the parent(s)/LAR(s) of the subject prior to performance of any study specific procedure. Where parent(s)/LAR(s) are illiterate, the consent form will be countersigned by an independent witness.
- A male or female between, and including, five and 17 months of age at the time of the first vaccination.
- Healthy subjects as established by medical history and clinical examination before entering into the study.
- Previously received three documented doses of diphtheria, tetanus, pertussis, hepatitis B vaccine (DTPHepB), and at least three doses of oral polio vaccine.

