6.6.5. Collect demographic data

Record demographic data such as date of birth and gender in the subject's eCRF.

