7.3.1.3. Measure of prevalence (*P. falciparum* infection)

The prevalence of *P. falciparum* infection will be evaluated on the cross-sectional ADI samples only. At each pre-defined timepoint (see protocol section 6.5) the prevalence (number of subjects with *P.falciparium* infection/total number of subjects) of *P. falciparum* infection will be calculated by group together with 95% CIs. Graphical presentations of the prevalence over time will be produced. Results per site and overall will be summarized in tables. In addition the number of positive prevalent infections will be analyzed by a negative binomial regression to compare the groups (Fx012-14, Fx017-20, R012) against the control to obtain vaccine efficacy estimates and corresponding 95% CI (applying the same strategy as for all episodes in section 7.3.1.2).

The prevalence of gametocytemia will be tabulated for each group (Fx017-20, Fx012-14, R012-20, R012-14 and control) at each monthly cross-sectional visit (from M0 until M20) and thereafter at each three-monthly cross-sectional visit (from M23 until M50).

Within gametocytes positive slides the mean male/female ratio will be tabulated by group and time point and by site. Within parasitemia positive subjects the geometric mean will be tabulated by group and time point and by site.

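### Three risk-window rules in SAP Tables 4 and 5 contradict their own row labels, and the second alpha-controlled test, whose windows lie 5 months apart, has no sensitivity analysis for age or period

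*SAP*

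**What the plan says.** **The test.** SAP Section 8 controls alpha for the primary objective and, hierarchically, for one secondary comparison: fractional third dose at Month 7 versus three full doses over 12 months post-dose 3. Section 7.3.1.6 and Table 5 run it as Fx017-20 over M7.5-M19 against R012-20 + R012-14 over M2.5-M14.

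**The model.** Section 7.3.1.1 covers unequal calendar periods, "as is done for comparison Fx017 versus both Fx012 and R012 during the period 7 and 12 months post dose 3". Its covariate statement is: "The following covariates are considered to be prognostic for clinical malaria: monthly prevalence of parasitemia for control group and study site". Section 11.1.4.4 requires every covariate to be listed in the SAP body, so an age term cannot be implied. Protocol 11.7.1 had instead defined incremental efficacy as a ratio of reductions against Control over matching periods. SAP Section 10 discloses the replacement without giving a reason.

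**The arms.** One sentence of 7.3.1.1 reads: "An analysis comparing the treatment schedules Fx017-20 versus Fx012-14 and R012-14 with respect to clinical malaria and incident infection". That leaves out R012-20, which the rest of the SAP pools with R012-14.

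**The windows.** Tables 4 and 5 define start and end of risk for each child. Table 4 is for comparisons with equal calendar times, Table 5 for unequal ones.

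**The concern.** The start and end columns are what a programmer implements. Where they disagree with the row label, literal programming gives a different risk period from the intended one. In the M7.5 rows of Table 4 it also loses the same-period comparison that is a stated reason for having a Control arm (protocol 1.2.2).

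The second test has a separate weakness. Enrolment is by age at first dose: "A male or female between, and including, five and 17 months of age at the time of the first vaccination". Randomisation balances that age, but not age at the start of windows 5 months apart. Any difference in malaria risk due to age or period that the Control-prevalence covariate does not capture is credited to the schedule, in a test presented as error-controlled. The SAP does not say whether Control prevalence is indexed by calendar month or study month, or how a monthly value enters a per-child negative binomial model. Section 7.3.1.3 only tabulates it: "At each pre-defined timepoint (see protocol section 6.5) the prevalence" is calculated by group.

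**Working it through.** **1. Windows (no assumptions).** Control's doses are at Months 0, 1 and 2. Fx017-20's are at Months 0, 1, 7, 20 and 32 (SAP Section 10).

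- Table 4, M7.5 rows. The start rule for both arms is dose 3 + 14 days: M7.5 for Fx017-20, M2.5 for Control. To M14: 14 − 2.5 = 11.5 months for Control against 14 − 7.5 = 6.5. To M19: 16.5 against 11.5. The M26 to M50 rows carry the same 5-month excess.
- Table 4, [1-7] row. From dose 2 (M1) to the Month 14 visit − 1 is 13 months; the label implies 6. It runs 7 months past Fx017-20's third dose.
- Table 5, 12-month row. Only R012-20 stops by month; the other groups stop the day before the fourth-dose visit, which for Fx017-20 is Month 20. Using the allowed dose 3 to dose 4 intervals (protocol Table 14) less 14 days: Fx017-20 364 − 14 = 350 to 420 − 14 = 406 days; R012-14 336 − 14 = 322 to 392 − 14 = 378 days.

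**2. Effect of the window errors (assumed inputs).**

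- Table 5 stop: assume efficacy of 75% decaying with an 8-month constant. The mean of 1 − 0.75e^(−t/8) is 0.644 over 0.5-13 months post-dose 3 and 0.626 over 0.5-12, a ratio of 1.028 on the all-episode rate. First-episode Cox is little affected, because few comparators remain at risk in the extra month.
- Table 4 start, programmed literally: take a constant true efficacy of 42% (1 − 0.29/0.5) and 6-month enrolment. At ±60% seasonality, first-episode efficacy reads 12-62% to M14 and 39-45% to M19; at ±30% it reads 29-53% to M14. With 12-month enrolment there is no effect.

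**3. The plan's own power figure.** Protocol 11.4: 250 evaluable per group, 0.29 and 0.16/pyr, 2:1, at least 90% power for the primary comparison. Over 11.5 months, events = n(1 − exp(−rate × 11.5/12)): 121.3 (500 at 0.29) and 35.5 (250 at 0.16). Power is 94% (Schoenfeld), 91% (two proportions), 88% (Wald) and 90.5% (simulated Cox). The stated figure is reproduced. The rates give 1 − 0.16/0.29 = 44.8% rather than the stated 50%; I use the rates. No power is stated for the second test, so I apply the same inputs to it.

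**4. Sensitivity of the second test.** Age at window start is 5 + 7.5 to 17 + 7.5 = 12.5-24.5 months in Fx017-20, and 7.5-19.5 in the full-dose arms. Under no schedule effect, events are 121.3 and 60.7, and SE = √(1/121.3 + 1/60.7) = 0.157. If the later window has hazard ratio h for non-schedule reasons, one-sided error = Φ(−1.96 − ln h/SE):

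- h = 0.95: 5.1%
- h = 0.90: 9.9%
- h = 1.00: 2.5%
- h = 1.10: 0.5%, with Wald power falling from 88% to about 74%

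These values of h are assumptions, and they apply only once the primary objective is met.

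**5. Cost of an age term.** With age uniform over 5-17 completed months (variance 14.1), a 5-month shift adds variance 25/(events × 14.1). At the design rates, SE = √(1/121.3 + 1/35.5) = 0.191. In a two-arm model (156.9 events) SE becomes √(0.0364 + 0.0113) = 0.218 and power 78%. With Fx012-14 in the same model (192.4 events, if it also has 0.16/pyr), SE is 0.214 and power 80%. Simulation gives 91% falling to 78% (two arms) or 83% (three arms).

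**The case against.** **On the windows.** The intent is easy to read: the labels say 7½, Table 4 is for equal calendar times, and the text under Table 5 asks for a negative slide at M7 for incident-infection periods starting at M7.5. The Table 4 rows are Fx017-20 versus Control, which Section 8 treats as descriptive. All this stands and limits the consequence. It does not make the cells right: Table 4's booster rows do give Control a visit-based start, and the M7.5 rows do not.

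**On age.** A reader might infer that the missing age term invalidates the alpha-controlled test or favours Fx017-20. The documents do not support that.

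- They give no age trend, and if risk rises with age the test is conservative.
- The remark about "an intervention group with reduced exposure and a different build-up of blood-stage immunity over time" concerns Control versus vaccine in all-episode analyses. The preceding bullet says that the first-or-only analysis minimises that bias and "is assumed to be the best way to assess the biological effect of the third dose fractioning and spacing".
- Control children age too, so Control prevalence may absorb part of a shared trend. In a large-sample check with an assumed −2% per month shared trend and ±30% seasonality, indexing by calendar month, the present model's null hazard ratio was 0.95-1.03 and its error 1.7-5.1%.
- An age term is no clean cure. At ±60% seasonality the simulated null hazard ratio was 0.87-1.01 without it and 0.96-1.12 with it, a range no narrower. Fx017-20 children aged 19.5-24.5 months at window start have no comparators of that age, so the adjustment extrapolates linearly there.

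**On the dropped analysis.** Protocol 11.7.6 lists first-or-only Fx017-20 versus Control for clinical malaria over M7.5-M19. SAP 7.3.1.6 and Table 4 keep all episodes only, and neither 7.3.2.3 nor Section 10 lists the change. A reader might infer selective removal. The protocol's own rule for follow-up beyond Month 14 is all episodes, so the SAP follows one of two conflicting protocol statements. Section 7.3.2.6 also plans piecewise Cox models of this arm against Control.

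**Conclusion.** The three window rules are wrong as written; this rests on the text alone. The Table 4 errors lengthen Control's time at risk by 5 months in every M7.5 row and make the [1-7] row 13 months instead of 6. They affect descriptive comparisons with Control. The Table 5 error falls in the row of the alpha-controlled test, but matters little: negligible for first-episode Cox, about ×1.03 for all episodes under the assumed decay. The primary window, [2½-14], is consistent.

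The lack of any age or period check on the second test is a gap worth closing cheaply, not a demonstrated bias. An error of 5-10% requires an assumed later-window hazard 5-10% lower; the opposite sign gives 0.5%. Making age part of the confirmatory model would trade about 8 to 13 points of power for a partial correction, so it belongs in a sensitivity analysis. The endpoint naming, the arms named in 7.3.1.1, the prevalence indexing and the unlisted change are clarifications.

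**What to change.** **Correct:**

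1. Table 4, all M7.5 rows: start Control at the Month 7 visit + 14 days.
2. Table 4, [1-7] row: end at the Month 7 visit − 1.
3. Table 5, 12-month row: end Fx017-20 at the Month 19 visit − 1.

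**Add:** keep the present model as the alpha-controlled test. Report beside it (a) the Control-referenced ratio of protocol 11.7.1 and (b) a model with age at the start of the risk window. Age at dose 1 would not serve, because randomisation already balances it.

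**Clarify:** in Section 8 and 7.3.1.1 name first-or-only episode, primary case definition, PPS, and the pooled R012-20 + R012-14 arms. State how Control prevalence is indexed and how it enters the negative binomial model. List in Section 10 that first-or-only Fx017-20 versus Control for clinical malaria over M7.5-M19 was dropped, or restore it.

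**Cost:** SAP text and a little programming, with no new data. The protocol has sites "Record demographic data such as date of birth and gender in the subject's eCRF", and the Month 7 and Month 19 visits exist in every group. The age-adjusted estimate will have a wider interval and extrapolates where ages do not overlap; as a sensitivity analysis it leaves the power of the test unchanged.
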